Dental caries is a chronic disease, ranking among the most highly prevalent diseases in children. According to the Global Burden of Disease study in 2017,¹ untreated dental caries in the deciduous dentition was the 10th most prevalent condition globally, affecting 532 million children worldwide.² It is one of the most common infectious diseases of childhood which is evident from the fact that in children, it is 7 times more common than hay fever or allergic rhinitis and 5 times more common than asthma.³ Under severe conditions, the pain and discomfort associated with dental caries can affect the quality of life of children and may lead to acute and chronic infections, changed eating and sleeping habits, and an increased risk of hospitalization.^{4,5}

Among a variety of chemotherapeutic agents that have been tested for preventing and arresting caries. Silver diamine fluoride (SDF) has a proven antibacterial action⁶ and releases fluoride ions onto the applied tooth surfaces, therefore, assisting in enamel remineralization⁷. Recently, the promising results of published clinical trials have popularized the use of SDF throughout the world.^{8,9} Today, it is available for arresting caries as a simple, non-invasive, low-cost medication.^{8,10} The major drawback of SDF is the staining of carious tissue to dark black due to the oxidation of the ionic silver in its formulation, along with reversible slightly painful lesions in oral mucosa caused by accidental contact of the SDF solution with soft tissues, these lesions usually disappear within 48 hours.¹¹

New formulations of silver nanoparticles (AgNP) show potent antimicrobial properties against a wide variety of microorganisms.¹²⁻¹⁴ Haghgoo et al.¹⁵ suggested the incorporation of nanosilver in varnishes and reported increased antimicrobial properties against cariogenic microorganisms such as *streptococcus mutans* and *streptococcus salivarius*. Nanosilver fluoride (NSF) is an experimental formula obtainable as a yellow solution containing uniformly dispersed silver

nanoparticles and fluoride. It was developed to be an effective anti-caries agent that does not stain the porous dental tissues black as does SDF.¹⁶

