An assistant will be responsible for giving each participant a serial number that will be used for his/her allocation. A duplicate of this number will be kept in an opaque envelope indicating to which group the patient belongs. This envelope will be kept by a trial independent individual who will be assigned the role of opening it only at the time of intervention; so that the group to which the child is allocated is concealed from the investigator.

Grouping

Participants will be randomly and equally allocated to one of the two treatment groups:

- **Test group (NSF):** Twenty-five children meeting the eligibility criteria will receive Nanosilver fluoride.
- **Control group (SDF):** Twenty-five children meeting the eligibility criteria will receive 38% Silver diamine fluoride.

Blinding

The investigator will not be blinded to the treatment type as the SDF solution has a bluish tint and will stain the active caries lesions black, while the NSF solution has a yellowish tint and is not expected to stain the lesions. However, the participants, the statistician, and the microbiologist will be blinded to the treatment group.

Materials

PEG-coated nanosilver fluoride (50 nm average particle size) will be prepared in the Center of Excellence for Research in Regenerative Medicine and its Applications (CERRMA) at the Faculty of Medicine, Alexandria University).

Once all of the above characterization tests and cytotoxicity assays yield satisfactory results, fluoride will then be added. Ten ml of 22,600 ppm of 5% Sodium fluoride varnish will be added to the nanosilver particles in a light proof brown bottle, vigorous stirring will be performed to achieve uniform dispersion of the nanosilver particles.

- 38% silver diamine fluoride: Advantage Arrest, Elevate Oral care (8 mL bottle).*²⁸
- Gauze
- Mirror
- Cotton rolls and pellets
- Tweezers
- Ball ended probe
- Plastic dappen dish
- Petroleum jelly
- Microbrush

Materials for the microbiological assessment

- Microbrush
- Mitis Salivarius Bacitracin (MSB) agar (selective culture media for *S. mutans*), prepared according to the manufacturer's instructions.**
- Rogosa SL agar plates (selective culture media for *lactobacilli*), prepared according to the manufacturer's instructions.***

- Saline as a transport medium.
- Sterile test tubes.
- Sterile plastic Petri dishes.
- Anaerobic gas jar.
- Incubator. ***

* Elevate Oral Care, LLC, West Palm Beach, FL, USA.

** Difco Laboratories Inc, NJ, USA.

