- A microbrush will be dipped into the SDF and dabbed on the side of the dappen dish to remove excess liquid before applying the solution to only the affected tooth surface.
- No more than one drop of SDF will be used for each patient.
- The SDF will be allowed to dry on the lesion for 1 minute.³³
- Any excess will be removed with a cotton pellet to minimize systemic absorption.

After the application of fluoride agents, all of the children will be instructed not to drink or eat for 1 hour after the appointment, their parents will be asked to observe this instruction.²⁴ Additionally, for ethical considerations, teeth not treated with SDF or NSF or those showing signs of failure or any new carious lesions that will appear during follow-up period will be appropriately treated.

Microbiological Procedure

1. Sample dilution

All samples will be dispersed by vortexing for 30 seconds then 10-fold serially diluted using sterile saline. A measure of the dilution will then be used for traditional plate culturing methods.^{34,35}

2. Culture

Aliquots of 10 ml of each dilution will be inoculated into freshly prepared Mitis Salivarius agar and Rogosa agar media respectively, using a micropipette.

- Mitis Salivarius agar plates will be incubated anaerobically in an atmosphere containing 10% CO₂ at 37°C for 72 hours to detect *Streptococcus mutans* counts.
- Rogosa agar plates will be incubated aerobically at 37° C for 48 hours to detect *Lactobacilli* count.

3. Isolation and Enumeration

Following the predetermined incubation period, colonies grown on the specified media will be counted and represented as (CFU/ml). *Streptococcus mutans* will be identified based on their characteristic morphology on Mitis Salivarius agar plates. Similarly, *Lactobacilli* will be identified biochemically and microscopically on the basis of their morphology.

4. Colony count

The number of colonies will be determined and expressed as colony forming units using the following equation.³⁶

$$\text{CFU/ml} = \frac{\text{n}^{\circ} \text{ of colonies} \times \text{dilution factor}}{\text{Volume taken in ml (1)}}$$

STUDY OUTCOME

Treatment effect will be evaluated after one month by comparing:

- Microbiological assessment of colony forming units (CFU) of *Streptococcus mutans* and *Lactobacilli*.
- Caries activity according to ICDAS criteria.

Follow up

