All patients will be recalled after one month. On the day of the recall appointment, patient preparation will be done as mentioned before.

Outcome assessment

- Microbiological assessment will be done as mentioned before and CFU counts will be recorded.
- Lesion activity will be assessed according to the ICDAS criteria. Using a blunt ended probe, if the cavity is found to be shiny and feels hard on gentle probing of the dentin, it will be recorded as an inactive lesion. While if it remains soft or leathery on gentle probing, it will be recorded as an active lesion.

STUDY PLAN

[figure not shown]

Figure: flow chart of the study plan

STATISTICAL ANALYSIS

The statistical software SPSS version 27.0 for Windows will be used for data analysis. The outcome variable is the number of colony forming units (CFU) of *streptococcus mutans and lactobacilli*, and the number of arrested caries lesions after 1 month in both the SDF and NSF groups. The collected data will be recorded and statistically evaluated.

The Chi square test will be used to compare the difference between the two groups regarding change caries lesion activity, the T-test or the Mann-Whitney U test will be used to analyze the differences between the microbiological samples, Wilcoxon signed rank will be used to assess the changes over time in bacterial counts. Regression analysis will be used to assess the potential confounders such as gender, social status, and dietary habits. The data will be graphically presented with suitable graphs. The level of statistical significance will be set at 5%.

ETHICAL CONSIDERATIONS IN SUBJECTS INVOLVING HUMAN SUBJECTS

1. This research protocol will be approved by the Research Ethics Committee of Alexandria University Faculty of Dentistry (IORG 0008839-IRB No. 0359-12/2021). prior to any research-related activities.
2. All research activities involving human subjects will abide by the Declaration of Helsinki³⁷ and other ethical guidelines adopted by the Research Ethics Committee of Alexandria University Faculty of Dentistry.
3. Benefits:
 - It will provide a caries arresting treatment for young children with multiple active carious lesions using minimally invasive atraumatic procedures.
 - It will allow overcoming the disadvantages of silver diamine fluoride including black staining of the teeth and any clothes it contacts, soft tissue injury, unpleasant taste for children.

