 - Support the use of nanosilver fluoride as a more convenient and more economical substitute to silver diamine fluoride for caries arrest in the primary dentition.
4. Harms/Risks:

Nothing more than the standard of care and the risk of black discoloration with SDF treatment.
5. Privacy and confidentiality:

Each participant will be provided with a serial number that will only be accessible to the principal investigator. No data regarding the identity of the participants will be shared under any circumstances. All participants or their guardians must provide a written informed consent prior to any procedures.

DURATION OF THE STUDY

Study Activity	Month								
	1	2	3	4	5	6	7	8	9
Purchase material	✓	✓							
Patient recruitment	✓	✓	✓						
Treatment procedures				✓	✓				
Evaluation					✓	✓			
Patients will be examined for caries activity and samples will be collected for microbiological assessment									
Data collection and statistical analysis						✓	✓		
Thesis submission								✓	✓

REFERENCES

1. Kassebaum, N. J. et al. Global, Regional, and National Prevalence, Incidence, and Disability-Adjusted Life Years for Oral Conditions for 195 Countries, 1990-2015: A Systematic Analysis for the Global Burden of Diseases, Injuries, and Risk Factors. *Journal of Dental Research* 96, 380–387 (2017).
2. Bernabe, E. et al. Global, Regional, and National Levels and Trends in Burden of Oral Conditions from 1990 to 2017: A Systematic Analysis for the Global Burden of Disease 2017 Study. *Journal of Dental Research* 99, 362–373 (2020).
3. Touger-Decker, R. & van Loveren, C. Sugars and dental caries. *The American journal of clinical nutrition* 78, (2003).
4. El Tantawi, M. et al. Prevalence and data availability of early childhood caries in 193 united nations countries, 2007–2017. *American Journal of Public Health* 108, 1066–1072 (2018).
5. Oubenyahya, H. & Bouhabba, N. General anesthesia in the management of early childhood caries: an overview. *Journal of Dental Anesthesia and Pain Medicine* 19, 313 (2019).
6. Milgrom, P. et al. Topical silver diamine fluoride for dental caries arrest in preschool children: A randomized controlled trial and microbiological analysis of caries associated microbes and resistance gene expression. *J Dent* 68, 72–78 (2018).
7. Gao, S. S. et al. Arresting early childhood caries using silver and fluoride products – A randomised trial. *Journal of Dentistry* 103, (2020).

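### The Harms/Risks statement conflicts with the protocol's own account of SDF and NSF, and the plan records no adverse effect in either arm

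*Combined protocol and SAP*

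**What the plan says.** The whole of the Harms/Risks item (Ethical Considerations, item 4) is: "Nothing more than the standard of care and the risk of black discoloration with SDF treatment". It names no risk for NSF.

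Other sections say more:

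- **Introduction, on SDF.** Besides staining, it describes "reversible slightly painful lesions in oral mucosa caused by accidental contact of the SDF solution with soft tissues", usually gone within 48 hours.
- **Introduction, on NSF.** "Nanosilver fluoride (NSF) is an experimental formula obtainable as a yellow solution".
- **Materials.** The NSF "will be prepared in the Center of Excellence for Research in Regenerative Medicine and its Applications", so it is prepared locally.
- **Ethical Considerations, item 3 (Benefits).** "It will allow overcoming the disadvantages of silver diamine fluoride including black staining of the teeth and any clothes it contacts, soft tissue injury". The same list goes on to name an unpleasant taste.

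Study Outcome opens with "Treatment effect will be evaluated after one month by comparing" and lists two things: colony counts of the two organisms, and caries activity by ICDAS. Outcome assessment, Statistical Analysis and the evaluation row of the timetable cover the same two.

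**The concern.** Two problems are linked. First, the risk statement is narrower than the protocol's own description of the two products. Effects of SDF that are counted as reasons to prefer NSF under Benefits are missing from the next item, Harms/Risks, and the experimental product has no risk statement at all.

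Second, if the plan is followed as written, the trial ends with no harms data in either arm. The Benefits item nevertheless says that NSF overcomes staining, soft tissue injury and bad taste, and that the study will support NSF as the more convenient substitute. None of these is measured, so they would remain assertions, and nothing would have been learned about the tolerability of a locally prepared product in children aged 4 to 6.

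**Working it through.** The main check is textual. The plan gives no harm rate or other safety figure to reproduce. Arithmetic enters only in step 4, to show what recorded data could and could not say.

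**1. Harms/Risks against the rest of the protocol**

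| Effect or property | Stated elsewhere | In Harms/Risks? |
|---|---|---|
| Black staining with SDF | Introduction; Blinding; Benefits | Yes |
| Mucosal lesions or soft tissue injury with SDF | Introduction; Benefits | Not named |
| Unpleasant taste with SDF | Benefits | Not named |
| NSF experimental | Introduction | No |
| NSF locally prepared | Materials | No |

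**2. Is any adverse effect recorded?** Study Outcome, Outcome assessment, Statistical Analysis and the timetable contain no safety item. The ICDAS activity criteria for a code 5 lesion (Appendix I, Table 2) concern hardness and shine, so scoring activity does not record staining either. The nearest provisions are the promise to explain side effects to families (Method, first visit) and the promise to treat failing teeth or new caries (end of Intervention). The first is disclosure and the second is care; neither records an event.

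**3. Timing.** The mucosal lesions usually resolve within 48 hours, and the only recall is at one month. Examination at recall would probably miss them, so they would have to be asked about.

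**4. What recording could show.** Inputs from Sample size estimation: 25 children per group enrolled, 24 needed. The step from 24 to 25 allows for 1/25 = 4% loss.

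Exact upper 95% limit when 0 of n children have an event, two-sided: 1 − 0.025^(1/n).

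- n = 25: 1 − 0.025^(1/25) = 0.137
- n = 24: 1 − 0.025^(1/24) = 0.142

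The one-sided limits, 1 − 0.05^(1/n), are 0.113 and 0.117.

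Chance of seeing at least one case among 25 children at true rate p: 1 − (1 − p)^25. The rates are assumed for illustration; the documents give none.

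| Assumed p | Chance of at least one case |
|---|---|
| 1% | 0.22 |
| 5% | 0.72 |
| 10% | 0.93 |

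Recording would therefore probably reveal a common effect and would often miss a rare one.

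**The case against.** **Standard of care already covers SDF.** SDF is applied under the manufacturer's instructions and a professional guideline, so the phrase can be read as including its usual effects, among them transient mucosal lesions. This has some force and weakens the SDF half of the conflict. The reading is strained, because staining is also a usual SDF effect and is named separately. It does not help with NSF, which the protocol itself calls experimental.

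**Risk was not ignored.** This stands. The protocol excludes children under 10 kg and those allergic to silver, requires satisfactory cytotoxicity assays before use, protects the gingiva with petroleum jelly, removes excess product in both arms, and promises families an explanation of side effects. These are precautions and disclosure. They make the short Harms/Risks item less consistent with the rest of the document, and none of them produces data.

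**Staining, taste and soft tissue injury are not trial aims.** Also correct. The specific aims are bacterial counts and caries activity. The criticism is confined to the Benefits item, which asserts advantages that the trial will not measure.

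**Stronger readings that the documents do not support.** A reader might infer that NSF has never been tested in children. The reference list includes an earlier randomised trial of NSF in children and a randomised comparison of an NSF varnish with SDF; the Introduction claims novelty only for in vivo antimicrobial efficiency against SDF in primary teeth. A reader might also infer that families or the ethics committee were misinformed. The consent pages are not available and the flow chart is not shown, so the point is limited to the protocol text. Nor does the plan imply that harms will be zero: unrecorded events are unknown.

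**Conclusion.** The point holds as a conflict within the protocol together with a gap in data collection. The Harms/Risks item does not match the Introduction, Materials and Benefits text, most clearly for NSF, and no adverse effect is recorded in either arm. The trial's data therefore cannot support the asserted advantages on staining, soft tissue injury and taste.

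The effect is limited. The comparisons of bacterial counts and caries activity are untouched. Nor would recording harms turn this into a safety trial: zero events in an arm would be compatible with a true rate of up to about 14% (13.7% with 25 evaluable children, 14.2% with 24). The change is worth making because it is small and replaces no information with some, but it is not a condition for the main analysis to be valid.

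The conclusion assumes that the sections available are the complete outcome, assessment and analysis text.

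**What to change.** **Wording.** Reconcile the Introduction, Benefits and Harms/Risks. Harms/Risks should name the mucosal lesions and unpleasant taste already described for SDF, and state that NSF is experimental and locally prepared. Benefits should present the advantages of NSF as expected, unless they are measured.

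**Data.** At the existing application and one-month visits, record yes/no for:

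1. mucosal lesion or soreness since application (caregiver report at recall);
2. visible lesion staining;
3. taste complaint;
4. any other adverse event.

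**Analysis.** Report the number of children with each item by arm, with exact 95% confidence intervals, as descriptive data without hypothesis tests. Count children, since several lesions per child may be treated.

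**Cost and limits.** No extra visit is needed. The protocol does not describe its data collection form, so it is an assumption that adding a few items is easy. Short-lived lesions will depend on caregiver recall at one month. The examiner is unblinded and black staining may reveal the arm to families, so these reports are open to bias, and the write-up should say so. It should also say that an absence of events in groups of this size does not establish absence of harm.

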Appendix I

Table (1): ICDAS severity criteria³⁸

Score	Criteria
0	No change in enamel translucency with prolonged air drying
1	First visual change in enamel (after prolonged air drying)
2	Distinct visual change in enamel
3	Localized enamel breakdown or discolored enamel with no visible dentine involvement
4	Underlying dark shadow from dentine
5	Distinct cavity with visible dentine
6	Extensive distinct cavity with visible dentine

Table (2): ICDAS caries activity criteria³⁸

ICDAS code	Characteristics of Lesion	
	Active Lesion	Inactive Lesion
1, 2 or 3	Surface of enamel is whitish/yellowish opaque with loss of luster; feels rough when the tip of the probe is moved. Lesion is in a plaque stagnation area, i.e.: pits and fissures, near the gingival and approximal surface below the contact point.	Surface of enamel is whitish, brownish or black. Enamel may be shiny and feels hard and smooth when the tip of the probe is moved. For smooth surfaces, caries lesion is typically located at some distance from the gingival margin
4	Probably active	
5 or 6	Cavity feels soft or leathery on gently probing the dentin	Cavity may be shiny and feels hard on gently probing the dentin.
